9.8.14. Study Drug Dispensation

Study drug will be dispensed to the patient along with the dosing diary and collected from the patient at the time points indicated in [Table 3](#).

9.8.15. Adverse Event Collection

Patients should be observed for general appearance, presence of illness or injury, or signs indicative of a concurrent illness at the time points indicated in Table 3. Patients should be instructed to volunteer any information regarding AEs at any time during the study, or query the patients with an open question regarding any AEs they may be experiencing (e.g., “How do you feel?” or “How have you been feeling since your last visit?”). Any findings are to be documented.

9.8.16. Clinical Chemistry

Samples will be collected for the following clinical chemistry analyses at the time points indicated in Table 3: urea nitrogen (BUN), creatinine enzymatic, total bilirubin, alanine aminotransferase (ALT), aspartate aminotransferase (AST), alkaline phosphatase, sodium, potassium, calcium, phosphorus, uric acid, cholesterol, total protein, albumin, chloride and bicarbonate.

9.8.17. Hematology

Samples will be collected for the following hematology assessments at the time points indicated in Table 3: hematocrit, hemoglobin, red blood cell (RBC) count, white blood cell (WBC) count, neutrophils, bands (if detected), lymphocytes, monocytes, basophils (if detected), eosinophils (if detected), absolute platelet count, mean corpuscular hemoglobin (MCH), mean corpuscular volume (MCV) and mean corpuscular hemoglobin concentration (MCHC).

9.8.18. Urinalysis and Microscopy

Samples will be collected for the following urinalysis assessments at the time points indicated in Table 3: specific gravity, ketones, pH, protein, blood, glucose, urobilinogen and bilirubin.

9.8.19. Chest Wall Separation

Chest wall separation measurements must be collected by CT scanning at the time points indicated in [Table 3](#). Institutions may use their local SOP for determination of chest wall separation as measured by CT. Chest wall separation will be reported in centimeters (cm).

9.8.20. Breast Volume

Breast volume measurements in patients that have undergone breast conserving surgery must be collected by CT scanning at the time points indicated in Table 3, which should correspond with the radiation treatment planning visit. Breast tissue should be defined per the [RTOG contouring guidelines \(RTOG 2009\)](#), but sites may use their local SOP for calculating breast volume.

9.8.21. Radiation Treatment

Planned radiation treatment must be no more than 7.5 weeks, and the dates of radiation treatment will be recorded in the eCRF at the time points indicated in Table 3. The dates of missed radiation treatment, the type of radiation treatment (regular radiation or boost treatment), and the use of a bolus will also be recorded in the eCRF. For patients for whom a bolus is used, an indicator other than redness of the skin surface (e.g., dosimeter at the skin surface) may be considered for decisions regarding radiation treatment dose and frequency.

9.8.22. Radiation Treatment Area

The surface area (cm^2) of the breast skin region treated with radiation must be measured and recorded as indicated in Table 3. The area (cm^2) of the breast skin area treated with radiation will be measured as defined in the study manual. The radiation treatment area surface measurements can occur at any time before Day 1 of radiation treatment.

9.8.23. Weigh Study Drug

The combined weight of the study drug and the lotion bottle (without box) must be recorded at the times listed in Table 3. Empty lotion bottles will not be provided to sites, and sites should not attempt to tare the scale with an empty lotion bottle before weighing. Study drug and lotion bottle weight should be recorded in units of grams, with 0.1 gram precision.

9.8.24. Pharmacokinetic (PK) Blood Samples

Blood samples for the determination of plasma RTA 408 and potential metabolite concentrations will be drawn at the time points indicated in Table 3. Blood sample collection instructions will be provided in the laboratory manual. The date and time of collection of all PK blood samples should be recorded; however, any deviations from the protocol-specified sampling times will not be considered protocol deviations. Sample time deviations will be summarized in the study report. Dates in the case report form should be recorded in an unambiguous format (e.g., DD MMM YYYY) and time should be recorded to the nearest minute (e.g., HH:MM using the 24-hour clock). Blood samples not drawn should be recorded as such. The date and time of the last two applications of study drug should also be collected on the PK case report form.

9.8.25. Dermatitis Assessment

The CTCAE v4.03 radiation dermatitis grade will be assessed by a local, trained physician, nurse or appropriately trained site staff member. Components of the CTCAE will be recorded separately by a local, trained physician, nurse or appropriately trained site staff member.

Dermatitis assessment at each visit is performed before initiation of radiation therapy. Dermatitis assessments must be performed by trained evaluator(s) at each time point indicated in [Table 3](#). These components include the severity of erythema, the extent and severity of dry desquamation, the extent and severity of wet desquamation and the presence of edema. Refer to Section [13.2.2.1](#) for the CTCAE scoring.

New or worsening of radiation dermatitis signs/symptoms should not be captured as individual AEs, but rather are captured in the Dermatitis Assessment process and documentation. These signs / symptoms are being assessed as study endpoints. Thus, if investigators seek to enter “radiation dermatitis”, “erythema”, “desquamation” or other signs / symptoms of radiation dermatitis as adverse events, they should first discuss the signs/symptoms with the medical monitor. The investigator, in coordination with the medical monitor, will determine the process for capturing these signs/symptoms.

9.8.26. Photographs of Radiation Treatment Area

Optional photographs may be collected at Sponsor-qualified sites at the times indicated in Table 3. The local, trained physician, nurse or appropriately trained site staff member who performs the dermatitis assessment should also collect photographs of the patient. Details of photography assessments will be outlined in a study specific manual. On Day 1 of radiation treatment and the last day of radiation treatment, photographs must be collected prior to radiation treatment.

9.8.27. Skindex-16 Assessment

The Skindex-16 quality-of-life tool will be used to assess patient responses to skin toxicity during and after radiation therapy at the time points indicated in Table 3. The Skindex-16 is a short 16-item patient-completed assessment using numerical analogue scales (0=never bothered to 6=always bothered). Responses to the Skindex-16 are categorized into three subscales: symptom, emotional and functional. The tool should be completed by the patient prior to initiation of that day’s planned radiation therapy. Refer to [Appendix B](#) for the Skindex-16 assessment.

10. STUDY DRUG MATERIALS AND MANAGEMENT

10.1. Study Drug

RTA 408 Lotion 0.5% or 3% and Lotion Vehicle will be used in this study. The investigational product consists of a preserved lotion formulation containing RTA 408 (0%, 0.5% or 3%), [REDACTED]

10.2. Study Drug Packaging and Labeling

The study drug will be supplied in a HDPE bottle with dispensing cap. [REDACTED] Bottles of study drug will be contained in a carton or kit.

The label on each kit and bottle will contain the following information:

- Protocol 408-C-1306
- Medication ID number
- Contents: 45 grams of RTA 408 Lotion or Vehicle
- SHAKE WELL PRIOR TO USE. FOR TOPICAL USE ONLY.
- Caution Statement: New Drug – Limited by Federal Law to Investigational Use.
- [REDACTED]
- Reata Pharmaceuticals, Inc., Irving, TX

10.3. Study Drug Storage

The stability of the drug product is being evaluated in ongoing studies.

Investigative sites must store the investigational product in a secure locatio [REDACTED]

[REDACTED] Sites must maintain a temperature log of the storage conditions.

Temperature logs must be available for review at each monitor site visit. When a temperature within the storage location at the site is noted to be outside the excursion range for 24 hours or more, or exceeds 40°C, the Sponsor must be notified.

10.4. Study Drug Administration

Please refer to Section 9.8.13 for details on study drug administration. Instructions will be provided to the patient regarding how to apply the lotion at each study drug administration time point listed in Table 3.

10.5. Study Drug Accountability

The investigator, or designee, will maintain a record of all study drug received, dispensed, and returned to the Sponsor or its designee. No study drug shall be destroyed by the clinical site

unless directed to do so by the Sponsor or its designee. All study drug containers will be weighed prior to dispensation and upon collection.

10.6. Study Drug Handling and Disposal

At the conclusion of the study, the Sponsor or its designee will direct the site regarding the final disposition of any remaining study drug.

11. PHARMACOKINETIC, PHARMACODYNAMIC, AND EFFICACY ASSESSMENTS

11.1. Pharmacokinetic Samples

Pharmacokinetic samples will be analyzed for RTA 408 using a validated analytical method. Samples may be analyzed for potential metabolites of RTA 408 using non-validated analytical methods.

12. SAFETY ASSESSMENTS

12.1. Safety Parameters

To avoid inter-observer variability, every effort should be made to ensure that the same individual who made the initial baseline determinations completes all safety assessments. Safety parameters include weight, BMI, vital sign measurements, physical examination results, adverse events, serious adverse events and laboratory test results (clinical chemistry, hematology, urinalysis and microscopy).

12.2. Adverse and Serious Adverse Events

12.2.1. Definition of Adverse Events

12.2.1.1. Adverse Event

An adverse event (AE) is defined as any untoward medical occurrence in a patient regardless of its causal relationship to study treatment. An AE can be any unfavorable and unintended sign (including any clinically significant abnormal laboratory test result), symptom or disease temporally associated with the use of the study drug, whether or not it is considered to be study-drug related. Included in this definition are any newly-occurring events or previous condition that has increased in severity or frequency since the administration of study drug.

New or worsening radiation dermatitis signs/symptoms should not be captured as individual AEs, but rather are captured in the Dermatitis Assessment documentation as these signs/symptoms are being assessed as study endpoints. Thus, if investigators seek to enter “radiation dermatitis”, “erythema”, “desquamation” or other signs/symptoms of radiation dermatitis as adverse events, they should first discuss the signs/symptoms with the medical monitor. The investigator in coordination with the medical monitor will determine how these signs/symptoms are to be recorded.

All AEs that are observed or reported by the patient during the study (from the time of first dose until the final visit indicated in [Table 3](#)) must be reported, regardless of their relationship to study drug or their clinical significance.

12.2.1.2. Serious Adverse Event

A serious adverse event (SAE) is any AE occurring at any dose and regardless of causality that:

- Results in death;
- Is life-threatening;
- Requires inpatient hospitalization or prolongation of existing hospitalization;
- Results in persistent or significant incapacity or substantial disruption of the ability to conduct normal life functions;
- Is a congenital anomaly or birth defect in an offspring of a patient taking study drug;
- Is an important medical event.

The term "life-threatening" refers to an event in which the patient was at immediate risk of death at the time of the event. It does not refer to an event that hypothetically might have caused death if it were more severe.

Important medical events are those that may not meet any of the criteria defined above, however, they may be considered serious when, based upon appropriate medical judgment, they may jeopardize the patient and may require medical or surgical intervention to prevent one of the other outcomes listed in the SAE definition.

Pregnancy is not considered an AE; however, information will be collected for any pregnancies which occur during the study (from the time of administration of the first dose of study drug until the final visit indicated in [Table 3](#)). Certain pregnancy outcomes will require submission as an SAE. (See Section [9.7](#))

The investigator is responsible for reporting to Reata or designee all AEs and SAEs that are observed or reported by the patient during the study (from the time of first dose until the final visit indicated in Table 3), regardless of their relationship to study drug or their clinical significance. All SAEs reported or observed during the study must be followed to resolution or until the investigator deems the event to be chronic or the patient to be stable. Reata or designee may contact the investigator to obtain additional information on any SAE which has not resolved at the time the patient completes the study.

12.3. Eliciting Adverse Event Information

At every study visit, patients must be asked a standard, non-directed question, such as, "How do you feel?" or "How have you been feeling since your last visit?" to elicit any medically related changes in their well-being. They may also be asked if they have been hospitalized, had any accidents, used any new medications or changed concomitant medication regimens (including prescription drugs, over-the-counter medications, vitamins, herbal products and minerals). Responses to questions asked must be documented in the source documents.

In addition to patient observations, AEs must be documented for any clinically significant diagnosis resulting from abnormal laboratory test values, physical examination findings, or ECG abnormalities, or from other documents that are relevant to patient safety.

12.4. Assessment of Causality

The investigator must use the following classifications and criteria to characterize the relationship or association of the study drug in causing or contributing to the AE:

Unrelated: This relationship suggests that there is no association between the study drug and the reported event.

Unlikely: This relationship suggests that the temporal sequence of the event with study drug administration makes a causal relationship improbable and/or other factors also provide plausible explanations.

Possible: This relationship suggests that treatment with the study drug caused or contributed to the AE. That is, the event follows a reasonable temporal sequence from the time of study drug administration, and/or, follows a known response pattern to the study drug, but could have been produced by other factors.

Probable: This relationship suggests that a reasonable temporal sequence of the event with study drug administration exists and, based upon the known pharmacological action of the drug, known or previously reported adverse reactions to the drug or class of drugs, or judgment based on the investigator's clinical experience, the association of the event with study drug administration seems likely.

12.5. Assessment of Severity

The investigator will grade the severity of the AEs as Grades 1, 2, 3, 4, or 5 based on the National Cancer Institute (NCI) Common Terminology Criteria for Adverse Events (CTCAE), version 4.03. If the criteria in the CTCAE version 4.03 do not apply, severity should be defined as follows:

Table 4: AE Severity Grades

Grade	Description
1	Mild; asymptomatic or mild symptoms; clinical or diagnostic observations only; intervention not indicated
2	Moderate; minimal, local or noninvasive intervention indicated; limiting age-appropriate instrumental activities of daily living
3	Severe or medically significant but not immediately life-threatening; hospitalization or prolongation of hospitalization indicated; disabling; limiting self-care activities of daily living
4	Life-threatening consequences; urgent intervention indicated
5	Death related to AE

The NCI CTCAE, version 4.03 will be provided to the investigator.

12.6. Recording Adverse Events

All conditions present prior to the first dose of study drug should be documented as medical history. Documentation of AEs shall continue until the final visit indicated in [Table 3](#), regardless of the relationship of the AE to study drug. Information to be collected includes type of event, date of onset, date of resolution, investigator-specified assessment of severity and relationship to study drug, seriousness, as well as any action taken.

While an AE is ongoing, changes in the severity (*e.g.*, worsening and improving) should be noted in the source documents but, when documenting the AE, only the total duration and greatest severity should be recorded in the case report form. AEs characterized as intermittent require documentation of onset and duration.

All drug-related (Possible or Probable, see Section [12.4](#)) AEs and abnormal laboratory test results reported or observed during the study must be followed to resolution (either return to baseline or within normal limits). All other AEs will be followed throughout the study.

AEs resulting from concurrent illnesses, reactions to concurrent illnesses, reactions to concurrent medications or progression of disease states must also be reported. Preexisting conditions (present before the start of the AE collection period) are considered concurrent medical conditions and should NOT be recorded as AEs. However, if the patient experiences a

worsening or complication of such a concurrent condition, the worsening or complication should be recorded as an AE. Investigators should ensure that the AE term recorded captures the change in the condition (e.g., “worsening of...”).

Each AE should be recorded to represent a single diagnosis. Accompanying signs (including abnormal laboratory test values or ECG findings) or symptoms should NOT be recorded as additional AEs. If a diagnosis is unknown, sign(s) or symptom(s) should be recorded as an AE(s). Changes in laboratory test values are only considered to be AEs if they are judged to be clinically significant (*i.e.*, if some action or intervention is required or if the investigator judges the change to be beyond the range of normal physiological fluctuation). If abnormal laboratory test values are the result of pathology for which there is an overall diagnosis (e.g., increased creatinine levels in renal failure), only the diagnosis should be reported as an AE.

[figure not shown]
New or worsening radiation dermatitis signs/symptoms should not be captured as individual AEs, but rather are captured in the Dermatitis Assessment documentation as these signs / symptoms are being assessed as study endpoints. Thus, if investigators seek to enter “radiation dermatitis”, “erythema”, “desquamation” or other signs / symptoms of radiation dermatitis as adverse events, they should first discuss the signs/symptoms with the medical monitor. The investigator in coordination with the medical monitor will determine how these signs/symptoms are to be recorded.

Elective procedures (surgeries or therapies) that were scheduled prior to the start of AE collection are not considered AEs. These elective procedures should not be recorded as AEs, but should be documented in the patient’s source documents as elective (e.g., elective periodontal surgery). However, if a pre-planned procedure is performed early (e.g., as an emergency) because of a worsening of the preexisting condition, the worsening of the condition should be captured as an AE.

12.7. Reporting Serious Adverse Events

Any AE the investigator considers serious according to the previously described criteria must be reported within 24 hours from the time when site personnel first learn about the event.

Table 5: SAE Reporting Contact Information

For questions regarding SAE reporting, contact your study manager, monitor, or

[figure not shown]
Any additional information that becomes available later should be submitted to the above number within 1 working day of receipt.

Reata or designee will notify regulatory agencies of any fatal or life-threatening unexpected events associated with the use of the study drug as soon as possible but no later than 7 calendar days after the initial receipt of the information. Initial notification will be followed by a written report within the timeframe established by the appropriate regulatory agency. For other SAEs that do not meet the fatal or life-threatening unexpected criteria, but are reported to be associated with the use of the study drug, Reata or designee will notify the appropriate regulatory agencies in writing within the timeframe established by those regulatory agencies. Reata or designee will provide copies of any reports to regulatory agencies regarding serious and unexpected SAEs to the investigators for review and submission to their institutional review board (IRB).

Principal investigators are responsible for informing their IRB of any SAEs at their site. SAE correspondence with regulatory authorities or IRBs must be submitted to Reata or designee for recording in the study file.

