13.2.2.1. Dermatitis assessment

The CTCAE v4.03 radiation dermatitis grade will be assessed by a local, trained physician, nurse or appropriately trained site staff member. Radiation dermatitis scoring will be evaluated as follows ([National Cancer Institute, 2010](#)):

Table 6: CTCAE Radiation Dermatitis Grade

Grade 0	No radiation dermatitis
Grade 1	Faint erythema or dry desquamation
Grade 2	Moderate to brisk erythema; patchy moist desquamation, mostly confined to skin folds and creases; moderate edema
Grade 3	Moist desquamation in areas other than skin folds and creases; bleeding induced by minor trauma or abrasion
Grade 4	Life-threatening consequences; skin necrosis or ulceration of full thickness dermis; spontaneous bleeding from involved site; skin graft indicated
Grade 5	Death

Components of the CTCAE will be recorded separately by a local, trained physician, nurse or appropriately trained site staff member. These components include the severity of erythema, the extent and severity of dry desquamation, the extent and severity of wet desquamation and the presence of edema.

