#### 7.1.6.1 Summaries of Adverse Events

Treatment-emergent AEs will be summarized by treatment at onset of the AEs. For each treatment, SOC, and PT, the number and percentage of patients reporting an event will be calculated. In summary tables, SOC will be presented alphabetically and events within SOC will be presented by decreasing frequency count based on the number of events in the total group.

Summary tables (number and percentage of patients) of AEs (by SOC and PT) will be provided by treatment as follows:

- All treatment-emergent AEs
- All treatment-emergent related AEs (probably or possibly related)
- All treatment-emergent AEs by severity
- All treatment-emergent serious adverse events (including deaths)
- All treatment-emergent adverse events leading to discontinuation of study drug

Listings will be provided showing:

- All AEs

- Serious adverse events (including deaths)
- AEs leading to discontinuation of study drug

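### Radiation dermatitis is left out of adverse event capture by default with no exception for serious cases, so a serious case has no assured 24-hour report, causality assessment or line in the SAE table

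*Protocol*

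**What the plan says.** **Exclusion.** Protocol 12.2.1.1 states: "New or worsening radiation dermatitis signs/symptoms should not be captured as individual AEs". Protocol 9.8.25 and 12.6 say the same, and SAP 7.1 repeats it. All four send these signs and symptoms to the Dermatitis Assessment, on the ground that they are study endpoints. None limits the rule by grade or by seriousness.

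**Way back in.** If investigators want to enter dermatitis as an AE, "they should first discuss the signs/symptoms with the medical monitor". Section 12.6 then adds: "The investigator in coordination with the medical monitor will determine how these signs/symptoms are to be recorded". Section 9.8.25 is similar: "The investigator, in coordination with the medical monitor, will determine the process for capturing these signs/symptoms". SAP 7.1 has no counterpart to this step.

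**Seriousness.** Protocol 12.2.1.2 defines an SAE as an AE that meets one of its listed criteria. These include death, a life-threatening event, and "Requires inpatient hospitalization or prolongation of existing hospitalization".

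**Expedited duty.** Protocol 12.7: "Any AE the investigator considers serious according to the previously described criteria must be reported within 24 hours". The clock starts when site personnel first learn of the event.

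**Scale.** Grade 4 in Table 6 (Protocol 13.2.2.1) begins "Life-threatening consequences; skin necrosis or ulceration of full thickness dermis". Grade 5 is death.

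**Tables.** SAP 7.1.6.1 builds its SAE table from treatment-emergent SAEs, and SAP 7.1.6.2 plans no further AE analysis.

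**The concern.** It is common to keep an efficacy endpoint out of the AE tables so that the same event is not counted twice. Such an exclusion normally stops where an event becomes serious. Here no sentence sets that limit, and the endpoint scale runs into outcomes that the protocol elsewhere treats as serious.

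Safety is a primary objective (Protocol 6.1), and the lotion is applied to irradiated skin. Causality is a live question for these signs: in the Phase 1 study described in Protocol 5.1, mild erythema at the dose site was recorded as drug-related. If a serious dermatitis event stays only in the Dermatitis Assessment, nobody is required to judge its relationship to study drug. The sponsor's own duties to regulators in 12.7, including the limit of 7 calendar days for fatal or life-threatening unexpected events, depend on first receiving the report.

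**Working it through.** No arithmetic applies. The check sets the rules side by side and follows one event through them.

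**Step 1: is the event captured as an AE?** By default, no (9.8.25, 12.2.1.1, 12.6, SAP 7.1). It becomes one only if the investigator seeks to enter it, discusses it with the medical monitor, and the two settle on AE recording. The protocol gives no criterion for that decision, no deadline, and no statement that a serious event must be entered.

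**Step 2: is the 24-hour duty triggered?** The SAE definition in 12.2.1.2 and the duty in 12.7 both begin from an AE. If step 1 ends in no AE entry, neither is clearly engaged. If step 1 is still under discussion, the 12.7 clock may already be running, because it starts at first knowledge. The documents do not say which takes precedence.

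**Step 3: does the Dermatitis Assessment supply what is lost?** Three comparisons show that it does not.

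- *Content.* AE records hold relationship, seriousness and action taken (12.6). The dermatitis components are erythema, dry desquamation, wet desquamation and edema (9.8.25). Neither hospitalisation nor causality is among them.
- *Identification.* Hospitalisation is an SAE criterion but is not part of any grade in Table 6. A patient hospitalised with grade 3 dermatitis could not be recognised as a serious case from the grade.
- *Timing and coverage.* SAP 3.1 bases summaries on scheduled visits, SAP 3.7.3 lets an unscheduled efficacy assessment stand in only for a missing scheduled one, and SAP 5.2.1 takes the maximum grade from weekly visits. A peak between visits can therefore be missed. Treatment codes are released after database lock (SAP 2.1), so the efficacy displays give no early signal by arm.

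**Step 4: does the event reach the SAE table?** Only if step 1 produced an AE that was judged serious (SAP 7.1.6.1). SAP 7.1, read alone, describes no way for that to happen.

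**The case against.** The strongest reply is that the protocol does provide a way in. A reader might infer that serious dermatitis is barred from AE reporting, that it has no place in the SAE tables, or that a site following 12.6 to the letter would report none of it. The text supports none of these. Section 12.6 includes the joint decision on recording. An event entered as an AE through that step and judged serious falls under the 24-hour rule and goes into the SAE table.

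Nor is there a flat contradiction. The AE definition that opens 12.2.1.1 is broad enough to include dermatitis, the exclusion concerns where signs and symptoms are recorded, and 12.2.1.2 makes the investigator responsible for reporting all AEs and SAEs. An investigator could satisfy every section at once.

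Further limits stand:

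- The exclusion covers signs and symptoms of radiation dermatitis, not skin events in general. An infection diagnosed separately can be its own AE under the single-diagnosis rule in 12.6.
- Grade 4 is not the same as an SAE. Section 12.2.1.2 restricts life-threatening to immediate risk of death, whereas grade 4 also lists items such as an indicated skin graft.
- A death is unlikely to go unnoticed, since it is also a reason for study termination (8.4.2).
- The grades are not lost. They appear in efficacy displays such as the bar chart by visit in SAP 5.2.2.

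These points narrow the concern but do not remove it. The monitor step depends on the investigator choosing to start it, has no criterion or deadline, comes before entry while the reporting clock may be running, and is absent from the SAP. With up to 35 centers, practice may differ between sites.

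**Conclusion.** The concern holds in this form: radiation dermatitis is excluded from AE capture by default, without an exception for seriousness, and entry depends on a discretionary discussion. Expedited reporting, causality assessment and SAE tabulation are therefore not assured for radiation dermatitis that is life-threatening, fatal or leads to hospitalisation. This is more than missing detail, because the default rule, followed as written, can produce that result.

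The size cannot be given as a number of events. The documents state no rate of serious dermatitis and no rate at which the monitor step leads to AE entry. The conclusion needs neither. It rests on two readings: that an SAE must first be an AE (12.2.1.2), and that the exclusion applies at every grade because no limit is stated. If the study manual or site training already contains an exception, the practical risk is smaller, but the protocol and SAP would still need to say so.

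**What to change.** Reconcile the passages by adding one sentence to Protocol 9.8.25, 12.2.1.1 and 12.6:

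*This exemption does not apply to radiation dermatitis that meets any criterion in 12.2.1.2; such events are recorded as AEs and reported under 12.7, and discussion with the medical monitor does not delay the report.*

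The sentence relies on the existing seriousness criteria and does not make every grade 4 an SAE.

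In SAP 7.1, state that such events are included in the AE and SAE summaries while their grades stay in the efficacy analysis. The SAP should cover tabulation only, since the instruction to sites belongs in the protocol.

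The cost is a short protocol amendment, a line in the SAP and a few more SAE reports. The efficacy endpoint and its analysis do not change.
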